1.1 Background and Hypotheses

The Italian population has moved away from the traditional Mediterranean diet and now predominantly follows a Western-style diet that is hypercaloric, rich in saturated fats, animal protein, and sugars (12). We hypothesize that a return to the original Mediterranean diet with modifications based on the scientific evidence of recent decades (longevity diet), and/or short periods of fasting-mimicking diet (5 days), can improve the overall health conditions of the population (9-11).

2. Objectives and Purpose of the Study

Primary Objective: To evaluate whether the longevity diet and the fasting-mimicking diet, either individually or in combination, can reduce the percentage of body fat in a cohort of subjects stratified by gender, age, body mass index, and defined physio-pathological states.

Secondary Objectives: To assess whether the longevity diet and the fasting-mimicking diet, either individually or in combination, can positively influence parameters related to the general health status of the analyzed sample, including (i) percentage of lean mass, (ii) phase angle as an indirect indicator of muscle function and cellular integrity, (iii) waist and hip circumference, (iv) total cholesterol, HDL, and LDL.

This is a retrospective, observational, single-center study to evaluate the effect of specific nutritional interventions (fasting-mimicking diet (FMD) and longevity diet (LD)) on reducing body fat. To achieve this, retrospective data from bioimpedance, anthropometric, and clinical analyses of subjects who underwent at least one of the two nutritional interventions (individually or in combination) at the Valter Longo Foundation in Milan from 2019 to 2022 will be analyzed. In particular, information from subjects who underwent at least two nutritional visits with bioimpedance analysis with a gap of at least 3 months between them will be considered. The subjects will be characterized based on (i) the type of nutritional intervention (FMD only, LD only, or combinations of LD and FMD); (ii) the duration of the nutritional intervention (short, medium, or long); (iii) the degree of obesity (normal weight, overweight, and obese); and (iv) physio-pathological status.

4. Data Collection and Analysis

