Data will be collected retrospectively from the electronic medical records of the Valter Longo Foundation. Bioimpedance analysis, anthropometric measurements, and clinical parameters including lipid profiles will be used to assess changes in body composition, body fat percentage, lean mass percentage, phase angle, waist circumference, hip circumference, and blood lipid levels.

5. Statistical Analysis

Statistical analyses will be performed using appropriate statistical software packages. Descriptive statistics will be used to summarize baseline characteristics, and paired t-tests or non-parametric equivalents will be used to compare pre- and post-intervention measurements. Analysis of variance (ANOVA) will be used to compare outcomes across different subgroups based on type of intervention, duration, degree of obesity, and physio-pathological status. Correlation analyses may also be performed to explore associations between changes in body composition and other variables. A p-value of less than 0.05 will be considered statistically significant.

6. Ethical Considerations

This study will be conducted in accordance with ethical principles and regulations governing clinical research. All data will be de-identified and handled in compliance with data protection regulations. Informed consent will be obtained from all subjects included in the study.

7. Conclusion

This retrospective clinical study aims to investigate the effects of the longevity diet and the fasting-mimicking diet, either individually or in combination, on body composition, age-related disease risk factors, and aging markers. The study will provide valuable insights into the potential benefits of these dietary interventions in promoting health and longevity, which could have significant implications for public health and wellness.

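### The between-diet ANOVA compares non-randomised groups without sex or age, although the primary objective names both as strata and no stated analysis uses them

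*Combined protocol and SAP*

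**What the plan says.** The design paragraph after the secondary objectives (Section 2) reads: "This is a retrospective, observational, single-center study to evaluate the effect of specific nutritional interventions". No allocation procedure is described. Subjects are grouped by the diet they followed: "i) the type of nutritional intervention (FMD only, LD only, or combinations of LD and FMD".

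The primary objective (Section 2) asks whether the diets reduce body-fat percentage "in a cohort of subjects stratified by gender, age, body mass index, and defined physio-pathological states".

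The design paragraph then lists four characteristics for each subject. The first is diet type and the second is duration; the list ends with "iii) the degree of obesity (normal weight, overweight, and obese); and (iv) physio-pathological status". Section 5 uses the same four for the group comparison: "ANOVA) will be used to compare outcomes across different subgroups based on type of intervention, duration, degree of obesity, and physio-pathological status".

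Section 5 names three other analyses:
- for baseline data, "Descriptive statistics will be used to summarize baseline characteristics";
- within subjects, "paired t-tests or non-parametric equivalents will be used to compare pre- and post-intervention measurements";
- optionally, "Correlation analyses may also be performed to explore associations between changes in body composition and other variables".

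A p-value below 0.05 is the only criterion for significance.

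**The concern.** Without randomisation, nothing makes the LD, FMD and combined groups alike in sex or age. A between-diet F-test then mixes any effect of diet with any effect of who chose or was offered it. The ANOVA is the only method named for comparing the diets, and sex and age are not in it. Entering all four listed factors in one model would account for obesity class and physio-pathological status, but not for a sex or age imbalance.

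The plan is also inconsistent with itself. The objective says the cohort is stratified by gender and age, and the analysis section never takes them up. At stake is a significant result by diet type that readers could take as a difference between LD, FMD and their combination.

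**Working it through.** **Text check.** The strata in the primary objective against the analyses stated in Section 5:

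| Stratum in the objective | In the ANOVA? | In another stated analysis? |
|---|---|---|
| Gender | No | Not named |
| Age | No | Not named |
| BMI | Yes, as obesity class | – |
| Physio-pathological state | Yes | – |

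Two of the four strata reach no stated analysis. No covariate, regression, matching or weighting is stated for the diet comparison.

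**Size.** The documents give no sample size, SD or baseline data, so there is no figure to reproduce and every input below is assumed.

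*Bias.* If women's change differs from men's by d points, the false difference between the two extreme groups is d × (difference in share of women):
- women 50/60/70% across the groups: 1 × 0.2 = 0.2 to 2 × 0.2 = 0.4 points;
- women 40/60/80%: 1 × 0.4 = 0.4 to 2 × 0.4 = 0.8 points.

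*Rejection rate in closed form.* Take a one-way ANOVA on change with no diet effect and residual SD 3. The noncentrality is λ = n × Σ(mᵢ − m̄)² / σ², where mᵢ = d × pᵢ, pᵢ is the share of women in group i, and σ² = 3² + d² × the average of pᵢ(1 − pᵢ).

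For women 40/60/80% and d = 2:
- The means are 0.8, 1.2 and 1.6, so Σ(mᵢ − m̄)² = 0.16 + 0 + 0.16 = 0.32.
- σ² = 9 + 4 × (0.24 + 0.24 + 0.16)/3 = 9.85.
- n = 100: λ = 32/9.85 = 3.25, and F(2, 297) rejects in about 34%.
- n = 30: λ = 9.6/9.85 = 0.97, and F(2, 87) rejects in about 13%.

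The same formula gives:

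| Women by group | d | n = 30 | n = 100 |
|---|---|---|---|
| 50/60/70% | 1 | 5.5% | 6.6% |
| 50/60/70% | 2 | 6.8% | 11.5% |
| 40/60/80% | 1 | 6.9% | 12.0% |
| 40/60/80% | 2 | 13% | 34% |

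*Simulation with all four planned factors in one ANOVA.* There is no diet effect. Women are 9 points higher in baseline fat. Age has SD 12 and adds 0.1 point of fat per year. BMI has mean 27 and SD 5 in every group, cut at 25 and 30. Four status classes and three duration classes are balanced across groups. Residual SD is 3. Six models of change were run for each pattern. In two, change falls by 0.1 or 0.2 per point of baseline fat, so the sex effect is 9 × 0.1 = 0.9 or 9 × 0.2 = 1.8 points. In the other four there is a direct sex effect of 1 or 2 points. Results for n = 100 per group, 3,000 runs each:

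| Pattern | Four planned factors | Plus sex, age and time between visits |
|---|---|---|
| Women 50/60/70%, equal age | 5.0% to 10.9% | 4.0% to 5.6% |
| Women 40/60/80%, equal age | 9.9% to 32.9% | 4.8% to 5.7% |
| Women 40/60/80%, mean ages 45/50/55 | 12.0% to 38.4% | 4.7% to 5.5% |

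At n = 30 per group, the four-factor ANOVA rejects in about 5% to 14% and the adjusted model in about 4% to 6.5%. Adding sex and age alone gives the same picture, because time between visits was unrelated to diet in the simulation. Simulation error near 5% is √(0.05 × 0.95/3000) = 0.4 points (one standard error). With no imbalance the rate is 5%.

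The adjusted model recovers 5% partly because no unmeasured confounder was simulated.

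**The case against.** **The between-diet test is not the primary question.** This stands. The objective asks whether the diets reduce body fat, with no hypothesis that one beats another. The paired tests address it, and each subject is their own control for stable traits such as sex. A reader might infer that the primary result is confounded by sex and age; the documents do not support that. The ANOVA by diet type is nevertheless planned at p < 0.05, and the missing strata belong to the primary objective itself.

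**The plan is silent rather than exclusive.** This also stands. Baseline summaries could include sex and age, the optional correlations could include age, and paired tests could be run within strata. A reader might infer that gender and age are shut out of every analysis; the text shows only that no stated analysis uses them. None of these routes would adjust the diet comparison.

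**The size has no anchor.** This stands in part. Imbalance, effect sizes and n are all assumed. The upper figures need both a marked imbalance and 100 subjects per group, and the lower end shows no inflation.

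**Baseline body fat.** A reader might infer that its absence is a further error. That does not follow. With assumed baseline SD 8, slopes of 0.1 to 0.2, a gap of 3 or 6 points between extreme groups and n = 100, the answer depends on the model. If all groups share one baseline line, ANOVA on change rejects in about 9% to 60% and baseline-adjusted ANCOVA in about 5%. If subjects regress to their own group's mean, ANOVA on change holds about 5% and ANCOVA rejects in about 9% to 66%. The documents do not show which applies.

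**Conclusion.** The point holds for sex and age in the between-diet comparison. The mismatch between the primary objective's strata and the analysis section is established from the text and needs no assumption. The inflation of the between-diet test is conditional: it needs an imbalance in sex or age across diets and a change in body fat that depends on it. The documents show neither, so a claim that the groups do differ would go too far. The simulated rates show direction and possible size only. They also assume that the ANOVA is run on change. Section 5 says only outcomes; if final values were meant, baseline differences would pass directly into the comparison.

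This is a cheap improvement to a secondary comparison, not a defect in the pre-post analysis.

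**What to change.** For the between-diet comparison, define the outcome as change between the two analysed visits, body-fat percentage first. Fit one linear model with diet group, sex, age, degree of obesity or baseline BMI, and physio-pathological status. Report adjusted differences with 95% CIs and describe them as associations.

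Add two sensitivity analyses:
1. Include the baseline value of the outcome, and say so if the result changes. In non-randomised groups neither version is always right.
2. Fit the model with and without duration and time between visits. Both are set after the diet starts and may be tied to diet type (Section 1 describes FMD as 5 consecutive days), so conditioning on them can itself bias the comparison.

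Report the paired pre-post results within the gender and age strata, and by BMI and physio-pathological state. Label them descriptive, because no multiplicity rule is stated.

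The cost is SAP wording, a little more analysis and a few degrees of freedom: two (one each for sex and linear age) if the planned ANOVA is already multi-factor, more if separate one-way ANOVAs were meant. Section 4 does not list sex and age among the data collected, but the objective's stratification already requires them. Unmeasured confounding remains.
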